Participants who complete twice daily administration of the assigned product on each study day between the Enrollment Visit (inclusive) and the Day 14 Followup Visit, as well as participants who adhere to one of the scenarios described above, will be considered adherent to the product use regimen. Participants who experience an AE that requires temporary suspension of product use at the instruction of the investigator for more than two days, but who are able to complete a total of 14 days of product use at the assigned frequency following resolution of the AE, prior to onset of the next menstrual period, also will be considered adherent. As well, participants who experience an AE that requires permanent product discontinuation, but completed daily administration at the assigned frequency on the days preceding the AE will be considered adherent.

For the sexually active cohorts (required to have vaginal intercourse at their usual weekly rate that must be at least twice per week), adherence is further defined as having at least two episodes of vaginal intercourse during the 14-day exposure period.

Non-adherent participants will be asked their reasons for non-adherence and this information will be recorded on study case report forms. If the participant is not willing to become adherent, the participant will be withdrawn from the study as described in Section 3.7. Non-adherent participants will not be replaced.

Note: Participants in the sexually active cohorts who have fewer than two episodes of vaginal intercourse between study Days 0 and 6 will be encouraged to resume their usual frequency of intercourse between Days 7 and 13.

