4.5 Toxicity Management

In response to AEs reported by study participants and/or observed upon exam by study staff, the investigator or designee will recommend either continuation or discontinuation of product use consistent with the criteria in Appendix II. Product use also will be discontinued in the event of pregnancy.

Participants who discontinue product use will not routinely be withdrawn from the study. Rather, every effort will be made to complete the safety evaluations scheduled to take place on study Days 7 and 14, and/or as specified in Appendix II.

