5.5 Day 14 Follow-up Visit for Female Participants

(target Day 14, allowable Day 12-16)

- Update locator information.
- Administer follow-up acceptability assessment and study burden assessment.
- Collect used and unused product applicators, review the participant's Daily Study Records, and obtain interval medical history to assess adherence with protocol requirements and determine whether any AEs occurred since the last visit.
- Collect urine and conduct pregnancy and LE test; if LE test is positive (greater than trace), perform culture and microscopy at the LL.

- Perform pelvic exam with colposcopy, as follows:
 - naked eye exam of external genitalia,
 - speculum exam of vagina and cervix,
 - colposcopic exam and imaging of vulva, vagina, and cervix,
 - vaginal pH,
 - dried smear for Gram stain,
 - wet mount for trichomonas, candida, and BV,
 - sno-strip and CVL for HIV viral load at the HPTN CL, and
 - bimanual exam for adnexal or fundal masses or tenderness.
- Follow up on any abnormalities observed according to Appendix II.
- Collect blood and perform CBC, liver and renal function testing, and coagulation testing at the LL; process plasma for HIV RNA PCR at the HPTN CL.
- Complete and submit required data collection forms.

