6.2 Adverse Experience Reporting Requirements

An AE is defined as any untoward medical occurrence in a clinical research participant administered an investigational product and which does not necessarily have a causal relationship with the investigational product. As such, an AE can be an unfavorable or unintended sign (including an abnormal laboratory finding, for example), symptom or disease temporally associated with the use of an investigational product, whether or not considered related to the product.

Study participants will be provided a 24-hour telephone number and instructed to contact the study clinician to report any AEs they may experience, except for life-threatening events, for which they will be instructed to seek immediate emergency care. Where feasible and medically appropriate, participants will be encouraged to seek medical care where the study clinician is based, and to request that the clinician be paged or otherwise contacted upon their arrival. With appropriate permission of the participant, records from all non-study medical providers related to AEs will be obtained and required data elements will be recorded on study case report forms. All participants reporting an AE will be followed clinically, until the AE resolves (returns to baseline) or stabilizes.

Site staff also will report all AEs that meet SAE reporting requirements according to the procedures set forth in the Study-Specific Procedures Manual and the time frames set forth in the DAIDS SAE Reporting Manual. Specifically, DAIDS-defined "intensive" reporting requirements will be followed for this study.

Active follow-up for safety outcomes (serious and non-serious AEs) in each study participant will end one day after the final application of study product, however all SAEs reported by participants during the study treatment period and/or during the eight-week period following the final application will be reported in accordance with the DAIDS manual. Information on all AEs will be included in reports to the US Food and Drug Administration (FDA), and other applicable government and regulatory authorities. Site staff will report information on all AEs and SAEs to their Institutional Review Board (IRB) in accordance with all applicable regulations and local IRB requirements.

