7.6 Data Analysis

All descriptive and inferential statistical analyses will be performed using SAS and StatXact statistical software. All randomized participants will be included in all analyses. In the text below, the term "treatment group" refers to a given frequency of a particular product, for sexually abstinent and sexually active participants separately. Secondary analyses will be performed that combine cohorts.

When the use of descriptive statistics to assess group characteristics or differences is required, the following methods are to be used: for categorical variables, the number and percent in each category; for continuous variables, the mean, median, standard deviation, quartiles, and range (minimum, maximum). Within-treatment group assessment of the change from the baseline measurement to the final follow-up measurement will be analyzed using McNemar's test (for categorical response variables) or the paired t-test (for continuous response variables). When the use of formal testing to assess differences between the control gel and CS gel arms is required, the following methods are to be used: for binomial response variables, chi-square tests and logistic regression; for continuous variables, t-tests and linear regression.

Control gel and CS gel participants within each cohort will be compared for baseline characteristics including demographics, pelvic examination, colposcopy, and laboratory measurements using descriptive statistics. Due to the small size of each cohort, formal comparisons will not be performed.

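### Section 6.2 ends active safety follow-up one day after the last application, which contradicts the Day 7 and Day 14 safety evaluations that Section 4.5 keeps for women who stop the gel early

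*Protocol*

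**What the plan says.** Section 6.2 sets the end of active safety follow-up by the last dose: "Active follow-up for safety outcomes (serious and non-serious AEs) in each study participant will end one day after the final application of study product". After that, SAEs that participants report "during the eight-week period following the final application will be reported in accordance with the DAIDS manual". The same section adds: "All participants reporting an AE will be followed clinically, until the AE resolves (returns to baseline) or stabilizes".

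Section 4.5 takes a different line for women who stop: "Participants who discontinue product use will not routinely be withdrawn from the study"; instead, "every effort will be made to complete the safety evaluations scheduled to take place on study Days 7 and 14", and/or the evaluations in Appendix II.

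Section 4.4 deals with non-adherence: "If the participant is not willing to become adherent, the participant will be withdrawn from the study as described in Section 3.7". Section 3.7 then asks for best efforts to obtain a final evaluation with the Section 5.5 content from women who leave before Day 14.

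The last scheduled visit in Section 5.5 has the window "target Day 14, allowable Day 12-16". Section 7.6 says: "All randomized participants will be included in all analyses". Section 7.6.1 likewise puts every enrolled woman in each primary tabulation.

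**The concern.** Two of the primary endpoints in Section 7.2.1, related pelvic or colposcopic findings and related Grade 3 or higher laboratory values, are found mainly by examination and testing. After enrollment, colposcopy and blood tests are scheduled only at Day 7 and Day 14. If active follow-up ends one day after the last dose, a woman who stops early can be past the cut-off before either visit.

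Appendix II stops product for findings such as deep epithelial disruption and generalized erythema, so some early stopping is toxicity-related by design. If one site records new non-serious findings at visits after stopping and another does not, both still count the woman in the denominator. Endpoint rates would then rest on different observation windows across four sites, in a Phase I study whose primary objectives are local and systemic toxicity.

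**Working it through.** **Timeline inputs.** Dosing lasts 14 days from Day 0 (Section 4.2), so the last application falls on Day 13 if none is missed. Section 4.4 allows make-up applications on up to two additional days after Day 13. The Day 7 visit window is Day 5–9 (Section 5.4) and the Day 14 window is Day 12–16 (Section 5.5).

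**Rule.** With L the day of the last application, active follow-up under Section 6.2 ends on E = L + 1.

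| L | E | Day 7 window (5–9) | Day 14 window (12–16) |
|---|---|---|---|
| 3 | 4 | opens 5 − 4 = 1 day after E | opens 12 − 4 = 8 days after E |
| 8 | 9 | inside | opens 12 − 9 = 3 days after E |
| 13 (no missed dose) | 14 | inside | Day 12–14 inside; Day 15–16 outside |
| 15 (two make-up days) | 16 | inside | inside |

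Section 6.2 therefore fits a woman who completes dosing and is seen on target. It does not fit early stoppers, and for a completer seen late it falls short by one or two days.

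**What is still captured after an early stop.**
- The event that led to the stop, if judged related, is already a primary endpoint (Section 7.2.1), and Section 7.6.1 counts each woman once in an event rate.
- AEs already reported are followed until they resolve or stabilize (Section 6.2).
- SAEs reported within eight weeks of the last application are reported (Section 6.2).
- Withdrawn women are asked for a final evaluation with Day 14 content (Section 3.7). If it takes place more than one day after the last dose, it too is past the cut-off.

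What remains open is a new non-serious event, exam finding or laboratory value that arises more than one day after the stop. This includes an endpoint of a different type from the one that caused the stop.

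**The plan's own figure.** For 12 women per arm (Cohorts 1 and 2), Section 7.3 uses P(0 or 1 endpoint) = (1−p)^12 + 12p(1−p)^11.
- p = 0.05: 0.540 + 0.341 = 0.882, which matches the stated 88 percent.
- p = 0.35: 0.00569 + 0.03675 = 0.0424, which matches the statement that it is below 0.05.

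**Illustration under assumptions.** The protocol gives no early-stopping rate. Assume m of the 12 women stop early and only a fraction f of their endpoint risk is recorded, while all 12 stay in the denominator. Then

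P(0 or 1) = (1−p)^(12−m)(1−fp)^m + (12−m)p(1−p)^(11−m)(1−fp)^m + m·fp(1−fp)^(m−1)(1−p)^(12−m).

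At p = 0.35:

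| m | f = 0 | f = 0.5 |
|---|---|---|
| 0 | 0.042 | 0.042 |
| 1 | 0.061 | 0.052 |
| 2 | 0.086 | 0.062 |
| 3 | 0.121 | 0.075 |

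The f = 0 column is an outer bound, because it also discards events before the stop and the event that caused it. If the visits are kept and their findings count, the 0.88 and 0.042 are unchanged.

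**The case against.** A reader might infer that early stoppers lose their Day 7 and Day 14 evaluations. The protocol does not say so. Section 4.5 keeps both visits on a best-effort basis, and the procedures in Sections 5.4 and 5.5 do not depend on current product use: each visit asks about AEs since the last one and includes colposcopy and blood tests. Section 7.6.1 tabulates endpoints seen during the study and does not mention the Section 6.2 window. This objection stands. The defect is a conflict over what counts, not a cancelled visit.

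A reader might also infer that women who stop for toxicity are counted as event-free, so that CS gel looks safer than it is. A woman who stops for related irritation already has an endpoint, so that reading fails in the most obvious case. The effect on the comparison has no known direction either. In the earlier Phase I study in Section 1.2, colposcopic findings occurred in 3 of 12 women on K-Y Jelly, the present control, against 1 of 12 and 2 of 12 on CS gel.

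Nor is the withdrawal rule in Section 4.4 aimed at women stopped by an AE. That section counts them as adherent if they had dosed as assigned until then.

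Finally, one event moves the printed upper 95 percent limit from 26.5% to 38.5% (n = 12), 30.9% to 44.5% (n = 10) or 45.9% to 64.1% (n = 6). Those shifts are general properties of small groups. They show what one event is worth, not what this rule costs.

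None of this reconciles Section 6.2 with Section 4.5. The cut-off applies to each participant without exception.

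**Conclusion.** The contradiction between Sections 6.2 and 4.5 is real for any woman who stops early. It leaves open whether new findings at her remaining visits count as primary endpoints, while Sections 7.6 and 7.6.1 keep her in the denominators. A completer seen on Day 15 or 16 is affected by one or two days.

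The possible loss is confined to new non-serious events, exam findings and laboratory values that arise more than one day after stopping. It occurs only if sites apply Section 6.2 literally. Its size cannot be estimated from the protocol. Under the assumed range of one to three early stoppers among 12, the probability of seeing 0 or 1 endpoint at a true rate of 35% would rise from 0.042 to between 0.052 and 0.121. This is an illustration, not an estimate.

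Section 4.4 also pulls against Section 4.5 for women who stop by choice and will not resume. For them Section 3.7 provides one best-effort evaluation at termination, not both scheduled visits.

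**What to change.** In Section 6.2, end active safety follow-up at the later of (i) the Day 14 or final visit and (ii) one day after the final application, and state that findings at those visits count as endpoints. The eight-week SAE rule and the follow-up of reported AEs can stay as they are.

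This is one wording change. The visits are already scheduled, so the cost is a few more recorded non-serious AEs.

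The Section 4.4 provision that withdraws non-adherent women who are unwilling to resume must be reconciled with Sections 4.5 and 3.7. How to do so is a participant-management decision for the study team, and no rule is proposed here.

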7.0 STATISTICAL CONSIDERATIONS

7.1 Review of Study Design

This is a multisite, Phase I, double blind, randomized, controlled comparison, frequency escalation study with 14 days of product exposure and follow-up.

7.2 Endpoints

7.2.1 Primary Endpoints

Consistent with the primary study objectives to assess the local and systemic toxicity of 6% CS gel versus the control gel on the vulvar and cervicovaginal mucosa of HIV-infected women, the following endpoints will be assessed among female study participants:

- Genital symptoms judged by the Investigator to be possibly, probably, or definitely related to product use.
- Pelvic exam findings, including colposcopic findings, judged by the Investigator to be possibly, probably, or definitely related to product use.
- Grade 3 or higher laboratory values (as defined by the DAIDS Toxicity Tables) observed among female participants for hematology, liver or renal function, and coagulation judged by the Investigator to be possibly, probably, or definitely related to product use;
- Adverse experiences judged by the Investigator to be possibly, probably, or definitely related to product use.

7.2.2 Secondary Endpoints

Consistent with the secondary study objective as listed in Section 2.2, the following secondary outcomes will be assessed:

- Participant "adherence" to the product use regimen, as defined in Section 4.4;
- Participant willingness to use the assigned study product during sexual intercourse in the future, as reported via the follow-up acceptability questionnaires.
- Reported positive aspects of using the assigned study product.
- Reported negative aspects of using the assigned study product.

7.2.3 Exploratory Endpoints

Consistent with the exploratory study objectives as listed in Section 2.2, the following secondary outcomes will be assessed:

- The number of copies of HIV RNA isolated from vaginal fluids at Screening, Enrollment, and Follow-up.
- Nugent score ^[14] for BV at Screening, Enrollment, and Follow-up.

7.3 Accrual, Follow-up, and Sample Size

As noted in Section 2.4 up to 96 female participants and up to 48 male partners will be included in this study. Female participants will be enrolled into four cohorts of 24 women each. Within each cohort, accrual of six participants at each of the four study sites is targeted. If for some reason a site experiences difficulty reaching its accrual targets, consideration will be given to shifting enrollment "slots" to the other sites, with prior approval of the Protocol Chair.

At each site, three of the six participants enrolled in each cohort will be assigned at random to apply CS gel at the assigned frequency (once or twice daily). The other three women will be assigned to apply the control gel. Also at each site, accrual of each cohort will proceed sequentially, after the completion of follow-up of all participants in the prior cohorts, provided accrual is not suspended per the provisions of Section 2.4.3.

As a means to characterize the statistical properties of this study, the following table presents the probability of observing zero, at least one, and two or more safety endpoints among groups of 12 women for various "true" event rates:

Event Rate	P (0 events n=12)	P (≥1 event n=12)	P (≥2 events n=12)
1%	0.89	0.11	0.01
5%	0.54	0.46	0.12
10%	0.28	0.72	0.34
15%	0.14	0.86	0.56
25%	0.03	0.97	0.84
35%	0.01	0.99	0.96
45%	< 0.01	>0.99	0.99

For example, if the true rate of a given endpoint is five percent, the probability that the endpoint will be observed in at least one of 12 women is 0.46. In addition, with a true rate of five percent, 12 women provide 88 percent power to exclude endpoint rates greater than 35 percent (i.e., the probability of observing 0 or 1 endpoint is less than 0.05 when the true rate is 35 percent, while this probability is 0.88 when the true rate is five percent).

The statistical properties of this study also may be characterized by the width of confidence intervals (CI) around observed event rates. The following table presents the exact 95 percent CIs around endpoint rates when zero, one, or two endpoints are observed among 12 women:

No. Endpoints Observed	Lower Bound of CI	Upper Bound of CI
0	0.0%	26.5%
1	0.2%	38.5%
2	2.1%	48.4%

The properties described above are fairly robust relative to possible nonadherence to the study treatment regimen (as defined in Section 4.4). For example, if two women per cohort were non-adherent to the regimen, a subgroup analysis of the 10 adherent participants in the cohort would provide 74 percent power to exclude event rates greater than 45 percent for a given toxic event rate of 10 percent, and a pooled group of 20 participants would provide 74 percent power to exclude event rates greater than 25 percent for a given toxic event rate of five percent.

7.4 Random Assignment

Upon enrolling in the study, female participants will be assigned at random to apply either 6% CS gel or the control gel. Randomization will be stratified by cohort and by site to ensure equal balanced assignment to each product within each cohort at each site. Specifically, provided each site meets its accrual target of six women per cohort, three women per cohort at each site will be assigned to apply CS gel, and three women per cohort at each site will be assigned to apply the control gel.

The SDMC will provide each study site with four series of numbered, sealed, opaque envelopes containing the random assignments for each cohort. Site staff will assign the envelopes to participants sequentially, in the order in which they are enrolled in the study. The envelopes and their contents will be maintained in participants' study records. Each participant will be assigned a product code number. Using an unblinded list of product codes and assigned products, the pharmacist at each site will supply either 6% CS gel or control gel.

7.5 Blinding

Throughout the period of study implementation and data analysis, neither study staff nor participants will be informed of the participants' random assignments (except as specified in section 6.1). Both study products will be supplied in identical, single-use applicators packaged in individual white wrappers. Study staff and participants will be unblinded after all study visits and data analyses are completed. Individual exceptions may be considered by the Protocol Chair and Medical Officer in situations where product information may be needed to protect the safety of the participant. In emergency situations, if a participant experiences an SAE that, in the opinion of the Investigator requires immediate unblinding, the study site pharmacist may disclose the treatment assignment to the Investigator without obtaining prior concurrence of the Protocol Chair and Medical Officer.

7.6 Data Analysis

All descriptive and inferential statistical analyses will be performed using SAS and StatXact statistical software. All randomized participants will be included in all analyses. In the text below, the term "treatment group" refers to a given frequency of a particular product, for sexually abstinent and sexually active participants separately. Secondary analyses will be performed that combine cohorts.

When the use of descriptive statistics to assess group characteristics or differences is required, the following methods are to be used: for categorical variables, the number and percent in each category; for continuous variables, the mean, median, standard deviation, quartiles, and range (minimum, maximum). Within-treatment group assessment of the change from the baseline measurement to the final follow-up measurement will be analyzed using McNemar's test (for categorical response variables) or the paired t-test (for continuous response variables). When the use of formal testing to assess differences between the control gel and CS gel arms is required, the following methods are to be used: for binomial response variables, chi-square tests and logistic regression; for continuous variables, t-tests and linear regression.

Control gel and CS gel participants within each cohort will be compared for baseline characteristics including demographics, pelvic examination, colposcopy, and laboratory measurements using descriptive statistics. Due to the small size of each cohort, formal comparisons will not be performed.

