The statistical properties of this study **Cohorts 1 and 2** also may be characterized by the width of confidence intervals (CI) around observed event rates. The following table presents the exact 95 percent CIs around endpoint rates when zero, one, or two endpoints are observed among 12 women:

No. Endpoints Observed	Lower Bound of CI	Upper Bound of CI
0	0.0%	26.5%
1	0.2%	38.5%
2	2.1%	48.4%

The properties described above are fairly robust relative to possible non-adherence to the study treatment regimen (as defined in Section 4.4). For example, if two women per cohort **in Cohorts 1 and 2** were non-adherent to the regimen, a subgroup analysis of the 10 adherent participants in the cohort would provide 74 percent power to exclude event rates greater than 45 percent for a given toxic event rate of 10 percent, and a pooled group of 20 participants would provide 74 percent power to exclude event for a given toxic event rate of five percent.

As a means to characterize the statistical properties of Cohort 3, the following table presents the probability of observing zero, at least one, and two or more safety endpoints among groups of 6 women for various "true" event rates:

Event Rate	P (0 events	P (> 1 event	P (> 2 events
Event Kate	n=6)	n=6)	n=6)
1%	0.94	0.06	<0.01
5%	0.74	0.26	0.03
10%	0.53	0.47	0.11
15%	0.38	0.62	0.22
25%	0.18	0.82	0.47
35%	0.08	0.92	0.68
45%	0.03	0.97	0.84

For example, if the true rate of a given endpoint in Cohort 3 is five percent, the probability that the endpoint will be observed in at least one of 6 women is 0.26. In addition, with a true rate of five percent, 6 women provide 97 percent power to exclude endpoint rates greater than 59 percent (i.e., the probability of observing 0 or 1 endpoint is less than 0.05 when the true rate is 59 percent, while this probability is 0.97 when the true rate is five percent).

The statistical properties of Cohort 3 also may be characterized by the width of confidence intervals (CI) around observed event rates. The following table presents the exact 95 percent CIs around endpoint rates when zero, one, or two endpoints are observed among 6 women:

No. Endpoints Observed	Lower Bound of CI	Upper Bound of CI
0	0.0%	45.9%
1	0.4%	64.1%
2	4.3%	77.7%

As a means to characterize the statistical properties of Cohort 4, the following table presents the probability of observing ze ro, at least one, and two or more safety endpoints among groups of 10 women for various "true" event rates:

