7.6.1 Primary Analyses

The primary aims of the study are to assess the local and systemic toxicity of once and twice daily application of 6% CS gel versus a control gel among HIV-infected women. The control gel provides information regarding signs, symptoms and/or morbidity that may be attributed to normal variation and/or the study procedures or use of applicator rather than the investigational product being studied. Primary data analyses will tabulate the number of primary endpoints — listed in Section 7.2.1 — observed during the study, by study cohort and product assignment within cohorts. All participants who enroll in the study will be included in each tabulation. Individual participants will contribute once to the calculation of event rates.

Additional safety analyses will tabulate the number and type of AEs observed overall and by severity and relationship to product, by cohort and product assignment. AEs that lead to discontinuation of product use and/or study participation will be tabulated separately. The temporal relationship of product application and AE onset, and the duration of symptoms, also will be evaluated. Finally, baseline, Day 7, and Day 14 laboratory measures will be summarized and the change in function, defined as the difference between the baseline and Day 14 measurements, will be described.

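### Section 7.3 rests its claim of robustness to non-adherence on an adherent-subgroup toxicity analysis that Sections 7.6 and 7.6.1 rule out

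*Protocol*

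**What the plan says.** Protocol Section 7.3 characterizes each product arm of 12 by the chance of seeing 0 or 1 endpoint: "12 women provide 88 percent power to exclude endpoint rates greater than 35 percent" when the true rate is 5%. It then says these properties hold up reasonably well under non-adherence as defined in Section 4.4. The support is an example: "if two women per cohort were non-adherent to the regimen", then "a subgroup analysis of the 10 adherent participants in the cohort would provide 74 percent power to exclude event rates greater than 45 percent" at a true rate of 10%. A second example reads "a pooled group of 20 participants would provide 74 percent power to exclude event rates greater than 25 percent" at a true rate of 5%. The letter of amendment of 1 August 2003 (item 6) keeps the single-cohort example, "a subgroup analysis of the 10 adherent participants in the cohort would provide 74 percent power", but limits it to Cohorts 1 and 2.

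The analysis section sets a different population. Section 7.6 says: "All randomized participants will be included in all analyses". Section 7.6.1, on the primary toxicity endpoints, says: "All participants who enroll in the study will be included in each tabulation". Section 7.6.2 treats adherence as a secondary outcome in its own right, not as a way of defining a toxicity analysis set. Section 4.4 adds that non-adherent women are not replaced, so they remain in the denominator.

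**The concern.** The sample-size section answers the threat of non-adherence by pointing to an analysis that the analysis section does not contain and, as worded, does not allow. A report could cite the 74% figure as reassurance although no planned analysis has that property.

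The direction matters because the primary objectives concern toxicity. A woman in the CS arm who used less gel than assigned probably carries less gel-related risk, yet counts fully in the denominator. The observed rate then falls below the rate among women who used the gel as assigned, and the error is toward apparent safety. The all-randomized set is a sound main set. The defect is that it is the only one permitted while Section 7.3 relies on another.

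**Working it through.** **Inputs.** From Section 7.3: arms of 12; the 0-or-1-endpoint criterion with error below 0.05 at the excluded rate; two non-adherent women, leaving 10; the 74%, 74% and 88% powers. The exposure and risk of the non-adherent women are not given in the protocol and are assumed below.

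**Step 1: reproduce the plan's figures.** Exact binomial, P(X ≤ 1) = (1−p)^n + n·p·(1−p)^(n−1).

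| n | True rate | P(X ≤ 1), power | Excluded rate | P(X ≤ 1), error |
|---|---|---|---|---|
| 12 | 5% | 0.882 | 35% | 0.042 |
| 10 | 10% | 0.736 | 45% | 0.023 |
| 20 | 5% | 0.736 | 25% | 0.024 |

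All three stated powers reproduce, so the arithmetic of Section 7.3 is correct. The difficulty is which analysis the second and third rows describe.

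**Step 2: match each figure to a planned analysis.** The n = 12 row corresponds to the tabulation in Section 7.6.1. The n = 10 row needs a tabulation restricted to adherent women. Section 7.6 does provide secondary analyses that combine cohorts, but these too include everyone randomized, so a pooled group of 20 (read here as 10 adherent women from each of two cohorts) is equally unavailable.

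**Step 3: what the all-randomized tabulation does under the same non-adherence.** Take 10 women at 35% and two at an assumed rate q. Then

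P(0 or 1 event) = (a0 + a1)(1−q)² + a0·2q(1−q),

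where a0 = 0.65^10 = 0.0135 and a1 = 10·0.35·0.65^9 = 0.0725.

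| Assumption for the two women | q | P(0 or 1 event) |
|---|---|---|
| Full risk | 35% | 0.042 |
| Risk proportional to use, 12 of 14 days | 30% | 0.048 |
| 11 of 14 days | 27.5% | 0.051 |
| 10 of 14 days | 25% | 0.053 |
| 7 of 14 days (half risk) | 17.5% | 0.062 |
| 5% risk only | 5% | 0.079 |
| No risk (upper bound) | 0% | 0.086 |

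For example, at q = 17.5%: 0.0860 × 0.6806 + 0.0135 × 0.2888 = 0.0585 + 0.0039 = 0.062. The 0.05 level is reached at q of about 28%, that is 0.28/0.35 = 80% of full risk.

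**Step 4: size of the dilution at the upper bound.** With two of 12 at zero risk, the expected observed rate is the on-gel rate × 10/12: 35% appears as 29.2% and 25% as 20.8%. At a 25% on-gel rate, the chance of seeing two or more events falls from 0.84 to 0.76.

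**The case against.** The strongest reply is that this is a wording tension and little more. Four parts of it stand.

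- **Degree of non-exposure.** A reader might infer that the toxicity rates are diluted by women who hardly used the gel. Section 4.4 does not support that. A woman can be non-adherent after missing three of 14 days, or two days not made up, and one unwilling to become adherent is withdrawn. The zero-risk figure is therefore an upper bound, and with minor lapses the 0.05 level is kept or barely passed.
- **No decision rule.** A reader might infer that the trial will wrongly declare a rate excluded. Section 7.3 uses the 0-or-1 criterion only to describe the design, and Section 7.6.1 only tabulates.
- **Cohorts 3 and 4.** A reader might extend the error figures to these cohorts. The amended non-adherence statement covers only Cohorts 1 and 2. In the sexually active cohorts a woman can apply every dose and still be non-adherent because she had fewer than two episodes of intercourse.
- **Partial handling of exposure.** Section 7.6.1 examines the timing of application against AE onset and tabulates separately the AEs that lead to discontinuation. Section 7.6.2 reports adherence by treatment group. Readers will see how much non-use occurred.

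One further argument does not stand. A supportive adherent-set table is often left to a statistical analysis plan, but here the protocol states that everyone is in all analyses. A later plan that added the table would contradict Section 7.6, and one that omitted it would leave Section 7.3 unsupported.

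**Conclusion.** The inconsistency holds on the protocol's own text. For Cohorts 1 and 2, the 74% property offered as protection against non-adherence belongs to an analysis that Sections 7.6 and 7.6.1 exclude. This does not depend on how much non-adherence occurs.

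The consequence for the toxicity rates does depend on it. With two of 12 women non-adherent and a 35% on-gel rate, the chance of 0 or 1 event goes from 0.042 to about 0.05 for minor lapses, 0.062 at half risk and at most 0.086. Two of 12 is the protocol's own illustration; the risk levels are assumptions. The bias is modest over most of that range, but where it acts it is toward apparent safety on a primary objective. The point is worth correcting, and it does not undermine the all-randomized set as the main analysis.

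**What to change.** 1. In Section 7.6, reword the sentence so that all randomized participants are included in the main analysis of each endpoint.
2. In Section 7.6.1, keep the all-enrolled tabulation as the main one. Add a supportive tabulation of each primary toxicity endpoint, by cohort and product, among women adherent to product use under Section 4.4, with exact 95% intervals.
3. For Cohorts 3 and 4, define that set by gel use alone, without the intercourse-frequency criterion.
4. If the supportive tabulation is not wanted, remove the robustness statement from Section 7.3 and from the matching text of the August 2003 letter.

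Section 4.4 counts as adherent a woman who stopped for an AE after using the product as assigned, so the adherent set keeps those toxicity cases.

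Do not require both tabulations to exclude a rate before calling it excluded. With 10 adherent women, 0 or 1 event cannot exclude 35% (P = 0.086), so zero events would be needed. At a true 5% rate the power would then fall from 0.88 to about 0.95^10 = 0.60.

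The cost is one reworded sentence and one table from adherence data already collected. The downside is wider intervals (for one event, an upper limit of 44.5% with 10 women against 38.5% with 12) in a subset formed after randomization, which can only support the comparison between gels.
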